4.5 Partial Dates

As a general rule, no imputation of partial dates will be done.

However, in order to evaluate if an adverse event is treatment emergent or not and to evaluate if a medication is concomitant or not, the following rules will be applied.

For the adverse events:

- If only the day of the start date of the AE is missing, the missing day will be considered as the last day of the month. If this "imputed" date is after the date of last study treatment administration, "imputed" date will be equal to the date of last study treatment administration. However, the original variable will not be imputed and only a temporary variable will be created in order to perform the evaluation.
- If the day and the month of the start date of the AE are missing, the missing day and month will be considered as the last day of the year (i.e. 31DEC). If this "imputed" date is after the date of last study treatment administration, "imputed" date will be equal to the date of last study treatment administration. Again, the original variable will not be imputed and only a temporary variable will be created in order to perform the evaluation.
- If the date is completely missing the adverse event will be considered as treatment emergent.

For the concomitant medications:

• If only the day of the start date or end date of the concomitant medication is missing, the missing day will be considered as the last day of the month. However, the start date cannot be after the end date; in this situation, the start date will be the same as the end date. However, the original variable will not be imputed and only a temporary variable will be created in order to perform the evaluation.

TPL Version: 02

- If the day and the month of the start date or end date of the concomitant medication are missing, the missing day and month will be considered as the last day of the year (i.e. 31DEC). However, the start date cannot be after the end date; in this situation, the start date will be the same as the end date. Again, the original variable will not be imputed and only a temporary variable will be created in order to perform the evaluation.
- If the date is completely missing the medication will be considered as concomitant.

In patient data listings, the documented date as given in the CRF, i.e. without imputation, will be reported (e.g. XXMAR2014 in case of day missing, but month and year available).

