4.4 Calculated Variables

- Baseline is defined as the last non-missing value done before the first dose
 of any study treatment, i.e. date ≤ first dose. Assessments done on the date
 of study treatment administration are assumed to take place before the
 administration, unless specified otherwise.
- **Treatment-emergent** (TE) data are defined as values after the first dose of any study treatment, i.e. date ≥ first dose, and before or on 28 days after the last dose of any study treatment, i.e. date ≤ last dose +28 days

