9.3 Adverse Events

Adverse events (AEs) will be coded using the Medical Dictionary for Regulatory Activities and will be graded according to the National Center Institute Common Terminology Criteria for AEs (NCI-CTCAE criteria [v4.0] [3]). Adverse events will be analyzed in terms of their type, incidence, severity and relationship to the study treatment. Related AEs are defined as events with a relationship to study treatment equal to 'possibly related', 'probably related', or 'definitively related' or with missing relationship.

Adverse events in this section will be tabulated if they are treatment-emergent (TE), see definition in Section 4.4. Partial dates will be handled according Section 4.5.

A summary table will present the frequency of patients with at least one:

- TEAE
- TEAE related to monalizumab or ibrutinib
- TEAE related to monalizumab
- TEAE related to ibrutinib
- TEAE causing monalizumab or ibrutinib discontinuation
- TEAE causing monalizumab discontinuation
- TEAE causing ibrutinib discontinuation
- TEAE causing dose delayed of monalizumab
- TEAE causing monalizumab infusion interrupted
- TEAE causing dose reduction of monalizumab at the lower dose level
- TEAE causing dose reduction of ibrutinib
- TEAE causing dose interruption of ibrutinib
- Grade 3 or worse TEAE
- Serious TEAE
- Monalizumab or ibrutinib related serious TEAE
- Monalizumab related serious TEAE
- Ibrutinib related serious TEAE
- Fatal TEAE
- Fatal TEAE related to monalizumab or ibrutinib

In addition, tabulations of the number of patients who experienced TEAEs as well as severity of the events will be presented by SOC and PT, by grade, by dose and overall. Patients will only be counted once for each preferred term. In case a patient experienced the same event more than once, the worst severity will be presented.

The following tabulations will be presented:

TPL Version: 02

[figure not shown]
- All TEAEs
- Monalizumab or ibrutinib related TEAEs
- Monalizumab related TEAEs
- Ibrutinib related TEAEs
- TEAE causing monalizumab or ibrutinib discontinuation
- TEAE causing monalizumab discontinuation
- TEAE causing ibrutinib discontinuation
- TEAE causing dose reduction of monalizumab at the lower dose level
- TEAE causing dose reduction of ibrutinib
- Grade 3 or worse TEAE
- Serious TEAEs
- Monalizumab or ibrutinib related Serious TEAEs
- Monalizumab related Serious TEAEs
- Ibrutinib related Serious TEAEs
- Fatal TEAE

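### The SAP's partial-date cap counts an adverse event as treatment-emergent even when its recorded month or year lies wholly after the 28-day window

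*SAP*

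**What the plan says.** SAP 4.4 makes treatment-emergent status a matter of dates. Such "data are defined as values after the first dose of any study treatment, i.e. date ≥ first dose", and the window closes "before or on 28 days after the last dose of any study treatment, i.e. date ≤ last dose +28 days".

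SAP 4.5 gives special rules for incomplete dates, used "in order to evaluate if an adverse event is treatment emergent or not" (and, separately, whether a medication is concomitant). For AEs:

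- Day missing: the final day of the known month.
- Day and month missing: 31 December of the known year.
- In both cases, if the result is later than the last study treatment administration, the imputed "date will be equal to the date of last study treatment administration".
- Date wholly missing: the event counts as treatment-emergent.

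The imputed value is a working value only: "the original variable will not be imputed and only a temporary variable will be created in order to perform the evaluation". Listings show the date as recorded.

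SAP 9.3 connects the two sections. It restricts its tables to treatment-emergent events as defined in 4.4 and refers to 4.5 for partial dates.

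**The concern.** The reset has no limit on how far it moves a date and takes no account of the part of the date that is known. After it, no AE with a partial start date can lie beyond last dose plus 28 days, so the upper bound in SAP 4.4 has no effect on these events. That is sensible when the known month could include a day inside the window. It is not sensible when the whole month or year lies outside it, because the record already settles the question. Two events in one patient and one month could then be classified differently only because one has a day recorded.

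The tables affected carry the main safety results. Occurrence of AEs and serious AEs (SAEs) is a phase Ib primary endpoint (SAP 3.1.1.1), and SAP 9.3 tabulates treatment-emergent events only. Phase Ib tables are shown by dose level, with 3 to 6 patients each. One patient wrongly counted under a preferred term therefore moves that cohort's rate by 1/6 = 17 to 1/3 = 33 percentage points, or by 1/27 = about 4 points among 27 patients.

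**Working it through.** The plan gives no figure to reproduce on this point, so the check applies the rule as written.

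**Inputs.** Month-end or 31 December imputation and the reset to last dose (SAP 4.5); window from first dose to last dose + 28 days (SAP 4.4). The calendar dates below are assumed for illustration.

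**Rule.** D = last day of the known month (or 31 December). If D > last dose, set D = last dose. Treatment-emergent if first dose ≤ D ≤ last dose + 28.

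**Simple case.** Last dose 15 January, non-leap year; the window ends 12 February. Onset is recorded as June. The earliest possible onset is 1 June: 16 + 28 + 31 + 30 + 31 + 1 = 137 days after the last dose. The rule gives D = 30 June, resets it to 15 January, and flags the event.

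**One patient, several dates.** First dose 5 September 2016, last dose 10 March 2017; the window ends 7 April 2017.

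| Recorded onset | Earliest days after last dose | SAP rule | Could onset be in the window? |
|---|---|---|---|
| April 2017 | 22 | flagged | yes |
| May 2017 | 52 | flagged | no |
| September 2017 | 175 | flagged | no |
| March 2018 | 356 | flagged | no |
| 2018, year only | 297 | flagged | no |

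A complete date of 15 September 2017 in this patient is not treatment-emergent.

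**All last-dose days in one non-leap year (365), onset with day missing.** Entries are the number of last-dose days for which the event is flagged. The last column applies the cap only if the known month begins on or before last dose + 28.

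| Onset month | SAP rule | No cap at all | Conditional cap |
|---|---|---|---|
| Same as last-dose month | 365 | 347 | 365 |
| One month later | 365 | 1 | 336 |
| Each of 2 to 12 months later | 365 | 0 | 0 |

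The conditional-cap column can be checked by hand. The first of the next month is more than 28 days away only for last doses on the first 3 days of a 31-day month or the first 2 days of a 30-day month: 7 × 3 + 4 × 2 = 29, and 365 − 29 = 336. Two months on, the shortest gap is 29 days (31 January to 1 March), which is already outside the window.

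The no-cap column shows why the cap should stay in some form. Without it, month-end imputation would drop nearly all next-month events, although 336 of 365 could lie inside the window.

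**The case against.** The strongest defence is that SAP 4.5 is a pre-specified special rule that resolves doubt towards counting safety events, and that SAP 9.3 invokes 4.4 and 4.5 together. On that view the sections do not conflict; 4.5 is only blunt. This stands for ambiguous dates. It does not stand where the known month or year leaves no doubt to resolve.

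The second defence is that late events seldom reach the database. Protocol 4.3 follows withdrawn patients for at least 4 weeks after the last study drug, or until related events recover or stabilise, and then has the end-of-study visit. Protocol 6.5 also places that visit at premature discontinuation. For completers, SAP 3.2.3 plans ibrutinib to the end of in-study follow-up. Much AE collection therefore ends near last dose plus 28 days. This stands as a limit on frequency, but the gap is not closed. Protocol 3.4 has 12 months of follow-up after IPH2201 stops, Protocol 9.1.2 continues observation to end of study after early discontinuation, and Protocol 9.1.3.1 has possibly related SAEs notified even after the end-of-study visit.

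Third, the error is traceable. Listings keep the recorded date, and SAE listings show onset and the treatment-emergent flag. This also stands.

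A reader might go further and infer that every partial-date event after the last dose is misclassified, or that late events are being attributed to the study drugs. The documents support neither. Events in the last-dose month, and usually those in the next month, may truly fall inside the window. Relatedness is a separate investigator judgement (Protocol 9.1.1.4) that the date rule does not alter.

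**Conclusion.** The point holds in a limited form and is minor. Misclassification is certain only when the whole known month or year lies after last dose plus 28 days. For those events the rule as written always gives the wrong status, and always towards over-counting treatment-emergent AEs.

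The number is probably small but cannot be estimated, because the documents give no count of partial dates. An affected event needs a partial start date well after both drugs have stopped. This reads the last study treatment administration in SAP 4.5 as the last dose of either drug, matching SAP 4.4. If it meant the last monalizumab dose, more events would be moved, but most would be treatment-emergent anyway because of continuing ibrutinib.

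DLTs (first 8 weeks of phase Ib), causality assessments, efficacy and sample size do not depend on this rule.

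**What to change.** In both AE bullets of SAP 4.5 (day missing; day and month missing), apply the reset only if the known month or year begins on or before the last dose of any study treatment plus 28 days. Otherwise keep the month-end or 31 December date, so that the event is not treatment-emergent under SAP 4.4. Refer to the last dose of any study treatment in both sections so that they use the same reference date. Leave the rule for wholly missing dates as it is, since there is no known part to check.

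The cost is one condition on a temporary variable, with no new data. Ambiguous dates keep their present inclusive handling.

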# 9.1 ADVERSE EVENT

#### 9.1.1 Definitions

The definitions of Adverse Events (AEs) and Serious Adverse Events (SAEs) are given below. It is the responsibility of the PI to ensure that all staff involved in the study are familiar with the content of this section.

The occurrences of AEs and SAEs are recorded from the time of signed informed consent until the end of the study. All AEs will be graded according to the Common Terminology Criteria for Adverse Events (CTCAE) of the NCI, version 4.03 (June 14, 2010).

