 - Bone marrow aspirate: the quality of this sampling, the normocellular status for age, the cellularity status and the percentage of nucleated cells for lymphocytes will be summarized
 - Bone marrow biopsy: the quality of this sampling, the normocellular status for age, the cellularity status, the percentage of nucleated cells for lymphocytes (by the categories specified in the CRF), the presence of nodules and the main composition of these nodules will be summarized
- Medical history will be tabulated by system organ class and preferred term with four separate tables for 'ongoing' and 'not ongoing' and for related and not related to CLL.
- ECOG performance status
- Baseline laboratory serology results: HIV, HCV, Hbs antigen and Hbs antibody
- Child-bearing potential (yes or no, and reason for non-child-bearing potential), contraception practice and pregnancy test result.

7. Prior and Concomitant Treatment and procedures

The number and percentage of participants receiving a prior or concomitant medication will be displayed by ATC level 4 and first Anatomical Therapeutic Chemical class (ATC 1) for the ITT/safety population. Prior medications are the medications that

Page 17 of 26

TPL N°: eTPL SA-02-01 Of SOP SA-02.08 TPL Effective Date: 31 Mar 2016

Version: 2.0

started and stopped before the date of first administration of the study drug. The concomitant medications will be grouped in two categories. The first group of concomitant medications corresponds to the medications which started before the date of first administration of study drug and which stopped on or after this date. The second group of concomitant medications corresponds to the medications which started on or after the date of first administration of study treatment and which stopped on or after this date. The medications with missing start and end dates will be classified in this last category. The prior medications and the two groups of concomitant medications will be displayed in three separate tables.

Concomitant procedures and surgeries will also be tabulated by system organ class and preferred term for the ITT/safety population.

8. Efficacy Evaluation

All the efficacy analyses are performed on both phases of the trial. The rates of remission (\S 8.1-8.4) will be assessed using the main endpoint population. The survival endpoints (\S 8.5) will be assessed in the ITT/safety population.

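### SAP 4.5 imputes late AE start dates without checking the AE end date, so an event over before first dose can count as treatment-emergent; some medicines begun before first dose may likewise be filed as started on treatment

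*SAP*

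**What the plan says.** **AEs.** For a start recorded only to the month, SAP 4.5 (Partial Dates) reads: "If only the day of the start date of the AE is missing, the missing day will be considered as the last day". When the month is missing as well, 31 December of the recorded year is used. The only limit is that the imputed start may not fall after the last study treatment. An AE with no date at all is taken as treatment-emergent. SAP 4.4 defines treatment-emergent as a date from first dose up to 28 days after last dose, with no condition on the end date. SAP 9.3 tabulates AEs only if they are treatment-emergent. Protocol 9.1.1 sets the collection window: "The occurrences of AEs and SAEs are recorded from the time of signed informed consent until the end of the study". Protocol 6.1 allows screening to begin up to 3 weeks before Week 0.

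**Medicines.** SAP 4.5 moves partial start and end dates to the end of the month or year in the same way, but adds a guard. In the year-only rule it reads: "the missing day and month will be considered as the last day of the year (i.e. 31DEC). However, the start date cannot be after". Its limit is the medicine's own end date, and a start that would exceed that limit is set equal to it. SAP 7 then makes three tables: prior; begun before first dose and continuing; and a third group defined as "the medications which started on or after the date of first administration of study treatment and which stopped on or after this date". For wholly undated medicines it adds: "The medications with missing start and end dates will be classified in this last category".

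The stated purpose of the imputation in SAP 4.5 is to decide whether an AE is treatment-emergent and whether a medicine is concomitant. Listings show the documented, unimputed dates.

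**The concern.** Late imputation of an AE start is normally defended as cautious: if the timing is unknown, count the event. That defence fails when the recorded end date shows that the event was over before dosing. The rule can then create a start later than the event's own end. The same section prevents this for medicines, so its absence for AEs looks like an oversight.

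Occurrence of AEs and SAEs is a phase Ib primary endpoint (Protocol 3.1.1, SAP 3.1.1.1), and the AE tables are given by dose. Dose levels hold 3 to 6 patients, so one wrongly flagged patient moves the count in a table row by 1/6 = 17 to 1/3 = 33 percentage points, if that patient has no genuine event in that row.

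For medicines, a late end date is a safe way to decide whether use overlapped treatment. A late start date does a different job in SAP 7: it can move a baseline medicine out of the table of those begun before first dose and into the table of those begun on treatment.

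**Working it through.** The plan states no figure that depends on this rule, so there is none to reproduce. The check applies SAP 4.4, 4.5 and 7 to test dates. First dose is **assumed** to be 15 June 2016 and last dose 14 June 2017.

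**1. AEs.** Flag = treatment-emergent if first dose ≤ imputed start ≤ last dose + 28 days.

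| Recorded start | Recorded end | Imputed start | Result under the SAP |
|---|---|---|---|
| June 2016 | 5 June 2016 | 30 June 2016 | treatment-emergent, though over 10 days before first dose |
| 2016 | 5 June 2016 | 31 Dec 2016 | treatment-emergent, same error |
| none | 5 June 2016 | none | treatment-emergent by rule, same error |
| May 2016 | any | 31 May 2016 | not treatment-emergent |

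The error therefore needs a start that is wholly missing, or known only to the month or year of first dose.

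**2. How often a partial pre-dose AE start is flagged.** Assume onset is uniform over the 21 days before first dose, and first dose is equally likely on any day of a 365-day year. There are 21 × 365 = 7,665 combinations.

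- Year only: onset falls in the previous year only for first doses on 1 to 21 January, which gives 21 + 20 + … + 1 = 231 combinations. Flagged share = 1 − 231/7,665 = 97%.
- Month and year: for first dose on day d of a month, min(d − 1, 21) of the 21 onset days share that month. The sums are 420 for a 31-day month, 399 for 30 days and 357 for 28 days. Flagged share = (7 × 420 + 4 × 399 + 357)/7,665 = 4,893/7,665 = 64%.

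These are shares of AEs with pre-dose onset *and* a partial start date. They include events still ongoing at first dose, for which the late date does not contradict a recorded end.

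**3. Medicines**, if the imputed date drives the SAP 7 split.

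| Recorded start | Recorded end | SAP 7 table | Correct if truly begun before 15 June 2016? |
|---|---|---|---|
| 2016 | ongoing | started on or after first dose | no |
| June 2016 | ongoing | started on or after first dose | no |
| 2016 | 2016 | started on or after first dose | no |
| May 2016 | ongoing | started before | yes |
| 2015 | ongoing | started before | yes |
| 2016 | 1 March 2016 or March 2016 | prior | yes, because of the guard |
| 2010 | 2010 | prior | yes |

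**4. How often an ongoing medicine is misfiled.** Assume the true start is uniform over the K years before first dose, and average over first-dose days spaced five days apart through the year. On average 180 days of the same year, and about 14.6 days of the same month, precede first dose. The share is 180/(365K) for year-only dates and 14.6/(365K) for month-year dates.

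| K (years) | Year only | Month and year |
|---|---|---|
| 1 | 49% | 4.0% |
| 2 | 25% | 2.0% |
| 5 | 10% | 0.8% |
| 10 | 5% | 0.4% |

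The longer a medicine has been taken, the less likely it is to be misfiled. Wholly undated medicines are outside this table because SAP 7 places them in the third group by rule.

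**The case against.** The AE gap is narrow. It needs a missing or partial start, an end before first dose, and, for a partial start, a month or year shared with first dose. Pre-dose collection lasts about 3 weeks, AE onset and end dates are recorded (Protocol 9.1.2), and queries must be resolved before database lock (Protocol 11.3.7). The error over-counts events, which is the cautious direction, and the listings show the dates as documented. All of this stands and keeps the point small. It does not justify calling an event treatment-emergent when its own end date rules that out.

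On medicines, SAP 4.5 says only that imputation decides whether a medicine is concomitant, and both later SAP 7 groups are concomitant. Use of the temporary date for the before/after split is therefore an inference, though the likely one. Nor does the SAP say whether an ongoing medicine counts as having a missing end date. Simply moving partial starts to the first day of the period would partly reverse the bias, by filing true on-treatment starts as earlier ones. These objections also stand.

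A reader might infer that pre-study medicines with partial dates are generally shown as started on treatment. The documents do not support that: an earlier start month or year, or an end that resolves to before first dose, is classified correctly. A reader might also infer that the third medicine table is the trial's signal for on-treatment events or prohibited drugs. Nothing says so: events come from the AE tables in SAP 9.3, and major deviations are summarised separately under SAP 5.2.

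**Conclusion.** The point holds in a limited form and is minor. As written, SAP 4.4 and 4.5 can count an AE with a recorded end before first dose as treatment-emergent. This follows from the text alone. The medicine point is conditional on the imputed date being used in SAP 7. It then covers only starts known to the month or year of first dose, with an end that is ongoing or does not resolve to before first dose. Wholly undated medicines go to the third group by explicit rule in any case.

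The number of affected patients cannot be given, because the documents do not say how many dates are partial. The percentages above are conditional on a partial date and on uniform timing, and are not forecasts for this trial. The complete-response endpoint and the rule of at least 4 responses in 27 patients do not use these dates and are unaffected. DLTs are tabulated separately under SAP 9.1.

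**What to change.** In SAP 4.5, apply to AEs the rule already used for medicines: an imputed start may not be later than the recorded end date. Add that an AE with a recorded end before first dose is not treatment-emergent, including when its start is wholly missing; capping an imputed start does not reach that last case. SAP 4.5 has no rule for partial AE end dates, so the sentence should apply only where the end certainly lies before first dose.

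In SAP 7, state which date drives the before/after split. Where a medicine's start is partial or missing, place it with those started before first dose if it was already recorded at screening or at Week 0 pre-dose.

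The cost is a few sentences and a small programming change. The medicine rule depends on the recording visit being available in the database, which the SAP does not describe. If it is not available, the AE change should still be made, and SAP 7 should at least say how unclear starts are handled.
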